### **1.4 Sample Size**

A sample size of 50 per group, two groups, for a total of 100 patients is the goal. An additional 15 patients will be enrolled to account for withdrawals, bringing total enrolled to 115.

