#### **3.2 Secondary Objectives**

- To evaluate the difference in pain from local anesthetic infiltration with J-tip needleless injection compared to needle injection by use of VAS.
- To evaluate efficacy of femoral nerve block after J-tip lidocaine injection post operatively by use of VAS.
- To assess patient and parent satisfaction with J-tip use by satisfaction questionnaire.
- To assess changes in post operative pain medication amounts with J-tip use.
  - 1) Type and amount in PACU
  - 2) Home log of amount taken daily for post operative days one through three (Standard opiate based pain medication prescription given to each patient). Measured in number of pills/tablets taken each day.
- To evaluate changes in post operative nausea and/or vomiting with J-tip use.
  - Calculated as “Present” or “Absent”
- To evaluate changes in post operative anti-nausea/anti-emetic medication use with J-tip use.
  - 1) Type and amount in PACU

- 2) Home record log of amount taken daily (Standard medication prescription given to each patient). Measured in number of pills/tablets taken each day.
- To evaluate time in PACU with use of J-tip compared to needle use group prior to regional block. PACU stay time recorded in minutes.

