Randomization to form the two trial groups will be performed by utilizing the computer program 'Research Randomizer' to create the randomization list. Randomization will be 50/50 or 1 to 1. The assignments will be printed out and placed into numbered envelopes.

The envelopes will be kept in a box in the [name] office. Group 1 will receive 0.25 mL of 1% buffered lidocaine delivered by the J-tip injector. Group 2 will be formed by subjects receiving 1.5 mL of 1% plain lidocaine injected by syringe and 25 gauge needle. The site of administration for this trial will be standard femoral and/or sciatic nerve block locations. The regional block will be performed under ultrasound guidance and with the assistance of nerve stimulation. General anesthesia will be given when the patient is in the operating room. This is done after the regional blocks have already been completed.

Administration of sedative and anxiolytic medications before or during the regional nerve block procedures will be based on nervous and pain VAS scores and anesthesiologist graded anxiety scores. If anxiety levels are indicated to be less than four, no sedation will be administered prior to the nerve block procedure. If anxiety scores are four to seven, then two mg to a maximum of four mg of Versed IV will be administered just prior to the local anesthesia administration. If anxiety scores are greater than seven, then two mg to a maximum of four mg of IV Versed will be administered just prior to the local anesthesia administration. If anesthesiologist observed anxiety levels remain above 7, then 20 mcg to a max of 40 mcg of IV Precedex will subsequently be administered.

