The current observations of clinical efficacy in the delivery of local anesthesia by either needle or J-tip introduction have shown that the superficial and subcutaneous tissues are adequately anesthetized. Pain is usually encountered as the touhy needle, nerve block needle, penetrates the fascia of the muscle. The fascia is a barrier to the deeper tissues and is not anesthetized with any local anesthetic. Additional medications may be administered during the needle insertion through the fascia during the regional block. If pain VAS is greater than four, and IV Versed was not administered due to anxiety scores between four and seven, then two mg to a maximum of four mg of IV Versed will be administered. If pain continues to be above four and IV Precedex was not administered due to anxiety levels greater than seven, then 20 mcg to a max of 40 mcg IV Precedex will be administered. If pain continues to be greater than four, then 25 mcg Fentanyl to a maximum of 50 mcg will be administered. If pain values continue to be above seven, then 100 mg of IV propofol will be given. No matter what amount and type of sedative or anxiolytic is administered during the nerve block procedure, the first VAS measure at each time point will be the one of record for analysis in this study.

Patients will indicate their level of nervousness by completing a visual analogue scale, after admission to the preoperative area, for how nervous they are prior to their procedure. The anesthesiologist through observational measurement on a scale of 0-10 will also measure patient anxiety levels. A level of ten will be the highest observed measure of anxiety. These scores will assist in identifying patients that may need more general types of anesthesia prior to the nerve block. This will also allow for further evaluation of limitations due to the amount of pre-op anesthesia of patients in the study.

Femoral nerve blocks will be performed on all arthroscopic procedures. Single injection sciatic nerve blocks will be utilized in addition to femoral catheter nerve blocks for patients undergoing arthroscopic surgery with ACL reconstruction or if lateral meniscus repair is expected to be performed. The site or sites of injection on the operative lower extremity will be chosen, a timeout taken and sterile preparation performed by the

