Times will be recorded for; time of J-tip administration, time of regional block performance, operating room arrival time, incision time, surgical end time, PACU arrival time and PACU discharge time. The amount of time from regional block to arrival in operating room and to incision time will be calculated. The surgical procedure time and amount of time in PACU will also be calculated.

Visual analogue pain scales will be completed prior to and immediately after J-tip use or needle local anesthesia infiltration. The scale immediately after will be with regard to pain felt at time of J-tip use or needle introduction. The scale will be completed once again prior to and immediately after needle introduction for each regional blockade. The scale immediately after will be with regard to pain felt at time of regional block needle introduction. Visual analogue pain scale will be recorded in PACU. All scoring will be performed on separate VAS assessments without patient access to previous scores.

The patient will record visual analogue pain scales on post-operative days one through three. The anesthesiologist will collect telephone verbal pain scores on a 0-10 scale on post-operative days one and two. This is current standard procedure for all patients who

receive a regional block. The femoral nerve block catheter, when utilized, is left in place for 40 hours from the initial femoral nerve block procedure. The number of days until the post-operative visit will be recorded. Another visual analogue pain scale will be completed at the first post-operative visit. An Arthroscopic Surgery Satisfaction Questionnaire will be completed by the patient and a parent or guardian at the first post-operative visit. The questionnaire will be specific to the patient's randomized treatment group. If the patient was randomized to receive the J-Tip, the patient and parent will receive the J-Tip questionnaire and if the patient was randomized to receive the traditional needle and syringe, the patient and parent will receive the needled syringe questionnaire. The sex of the parent or guardian completing the form will be recorded.

It will also be recorded if intra-articular analgesic injection is given intra-operatively. The amount and type of pain and anti-nausea/emeitic and pain medication use will be recorded in PACU and by the patient on the first three post-operative days.

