## **7. Statistical Analysis Plan:**

Analyses will vary by specific aim. To evaluate our hypotheses, we will use exact and non-parametric hypothesis testing procedures. Confidence intervals (95%) of differences will be computed. Regression analysis will be employed when adjustment between comparison groups is considered necessary.

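### No adjustment for planned procedure is prespecified in the post-operative comparisons, although it decides who has a 40-hour femoral catheter plus a sciatic block

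*Combined protocol and SAP*

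**What the plan says.** Any arthroscopic knee surgery at age 11 to 17 is eligible (Sections 1.2 and 5.1). Section 4 gives every patient a femoral block and then lets the planned operation decide the rest: "Single injection sciatic nerve blocks will be utilized in addition to femoral catheter nerve blocks for patients undergoing arthroscopic surgery with ACL reconstruction", and likewise where lateral meniscus repair is expected. On duration it says: "The femoral nerve block catheter, when utilized, is left in place for 40 hours from the initial femoral nerve block procedure".

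Section 3.2 compares the arms on post-operative VAS, PACU medication and PACU minutes, and on a "Home log of amount taken daily for post operative days one through three", with a similar log for anti-emetics. Section 4 adds patient-recorded VAS on days 1 to 3.

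On allocation, Section 4 says "Randomization will be 50/50 or 1 to 1" and describes a computer-generated list in numbered envelopes, with no strata. Section 7 plans exact and rank-type tests and then: "Regression analysis will be employed when adjustment between comparison groups is considered necessary". It names no covariate, outcome or trigger. The last objective in Section 1.7 lists BMI, thigh circumference, gender, ethnicity and operative time as factors to examine. Surgery and block type are not among them.

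**The concern.** Planned procedure is known before the skin injection, and it sets the analgesic regimen during the period when the post-operative outcomes are collected. Section 2 itself says that regional block reduces post-operative pain and opioid need, so the plan's own reasoning makes the regimen prognostic. By contrast, Section 2 presents a more effective block, and hence less medication, only as something that local anesthesia may allow.

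If such a factor stays in the error term, intervals are wider than they need to be. A chance difference in case mix can also pass for an effect of the injection method on pain or pill use. Leaving the choice of covariates open until after the data are seen adds a further degree of freedom.

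**Working it through.** **1. The plan's own figure.** "A sample size of 50 per group, two groups, for a total of 100 patients is the goal" and "An additional 15 patients will be enrolled to account for withdrawals, bringing total enrolled to 115": 2 × 50 + 15 = 115, which holds. The 50 per group cannot be reproduced, because no effect size, SD, alpha or power is stated. The only error-rate statement is "Confidence intervals (95%) of differences will be computed". A two-sided 0.05 level and a notional 80% unadjusted power are therefore assumptions below.

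**2. Does the regimen overlap the outcomes?** The block time of day is not given; assume 08:00 to 16:00. Forty hours from 08:00 ends at midnight closing post-operative day 1. Forty hours from 16:00 ends at 08:00 on day 2. The catheter spans PACU and day 1, reaches at most the early part of day 2, and does not reach day 3.

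**3. Size of the loss.** Let p be the share of patients with the factor and d its effect in within-stratum SDs. Neither is in the documents. For a continuous outcome in a linear model:

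- R² = p(1−p)d² / (1 + p(1−p)d²)
- equivalent sample-size factor = 1/(1−R²) = 1 + p(1−p)d²
- SD of chance imbalance = √[p(1−p)(1/n₁ + 1/n₂)]

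At 50 per group:

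| p | 95% imbalance (points) | gain, d = 0.25 | d = 0.5 | d = 0.8 | d = 1.0 |
|---|---|---|---|---|---|
| 0.5 | ±19.6 | 1.6% | 6.25% | 16% | 25% |
| 0.7 | ±18.0 | 1.3% | 5.25% | 13.4% | 21% |
| 0.8 | ±15.7 | 1.0% | 4.0% | 10.2% | 16% |
| 0.9 | ±11.8 | 0.6% | 2.25% | 5.8% | 9% |
| 1.0 | 0 | 0 | 0 | 0 | 0 |

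Example at p = 0.5, d = 1.0: R² = 0.25/1.25 = 20% and the factor is 1.25. The imbalance SD is √(0.25 × 0.04) = 0.10, and 1.96 × 0.10 = 0.196. An imbalance at that limit shifts the unadjusted difference by 0.196 within-stratum SD. The standard error is √1.25 × √0.04 = 0.224, so the shift is 0.88 standard errors.

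If unadjusted power were 80%, adjustment would raise it to 87.9% at p = 0.5, d = 1.0; to 82.3% at p = 0.5, d = 0.5; and to 80.2% at p = 0.9, d = 0.25.

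With the analysed 54 and 57 patients and p = 0.5, √[0.25 × (1/54 + 1/57)] = 0.095, or ±18.6 points.

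**4. Did block type vary among those analysed?** Table 1 gives a VAS after local sciatic infiltration for 54 needle and 57 J-Tip patients, the same counts as for femoral. Table 2 has 109 degrees of freedom, and 54 + 57 − 2 = 109. Recomputing the pooled t from the Table 1 summaries gives 5.079 against the printed 5.080 (sciatic), and 5.793 against 5.792 (femoral), so the counts are consistent with the tests. Taken at face value, all 111 had a sciatic block. Under the Section 4 rule they would also be catheter patients, which is the p = 1.0 row.

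**5. What was adjusted for.** The reported regressions cover only VAS after local infiltration. They include thigh circumference, ethnicity, age, gender and BMI beside injection type, with no surgery or block term. VAS prior to PACU discharge appears only in a list of comparisons of means.

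**The case against.** The strongest reply is that the factor seems constant where it matters. If all 111 analysed patients had both blocks, adjusting for block type gains nothing. The remaining contrast, ACL reconstruction against lateral meniscus repair, falls within one block regimen under Section 4, and the documents give neither its split nor any outcome difference. Larger surgery and the added block also come together, so their effects on pain may partly cancel. The outcomes are secondary, Section 7 does allow regression, and an unadjusted interval already allows for chance imbalance over repeated randomisation.

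Much of this stands, and it limits the size. It does not remove the point. The plan as written admits patients with a femoral block only. Catheter use and procedure mix are not reported. When regression was used, five characteristics were chosen and planned procedure was not among them.

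A reader might go further in several ways that the documents do not support:

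- That the comparisons are biased. Under 1:1 randomisation they are not, on average.
- That day 1 to 3 outcomes were analysed unadjusted. Those results are not in the document; only the lack of prespecification can be shown.
- That the gain is large. A gain of 11% to 33% needs an R² of 10% to 25%. A spurious 0.2 to 0.4 VAS points needs a 2-point effect (2 × 0.10 to 2 × 0.19) with the factor present in half. All of these are assumed inputs.
- That the catheter covers much of day 2. Step 2 of the working shows otherwise.
- That planned procedure is already a study data item. Section 4 does not list it, though it must be known to choose the block.

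**Conclusion.** The point holds as a gap in prespecification, for secondary outcomes only. Planned procedure determines the early post-operative regimen, is not described as a stratification factor, and is not named as a covariate.

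The cost is lost precision and uncorrected chance imbalance, and its size rests on assumptions: about 0.6% to 25% equivalent sample size for p = 0.5 to 0.9 and d = 0.25 to 1.0, and ±12 to ±20 points of imbalance at 50 per group. The sample-size figures apply to continuous outcomes in linear models and do not carry over directly to skewed pill counts, yes/no outcomes or rank tests. For block type the cost is zero if all 111 had both blocks. ACL reconstruction against other surgery may still vary, by an amount the documents do not give. This is an inexpensive improvement and does not undermine the trial's main comparison.

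**What to change.** Add to Section 7 that the post-operative comparisons (PACU and day 1 to 3 VAS, pill counts, anti-emetic use, PACU minutes) account for one factor with non-overlapping levels: planned procedure as known before randomisation. Possible levels are ACL reconstruction; lateral meniscus repair without ACL reconstruction; and other surgery with femoral block only. Enter it as a covariate in regression or as the stratum in a stratified rank or exact test, collapse empty levels, and take the 95% interval from the same analysis.

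Report the factor's distribution by arm. If it does not vary, that table settles the matter.

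Do not substitute operative time, and use intra-articular injection only in a sensitivity analysis, since both arise after randomisation.

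The cost is a few lines of SAP text and one variable, which should be obtainable from the surgical plan or chart. No change to treatment, visits or sample size is needed.

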## **5. Study Population:**

The 15 patients enrolled to account for withdrawals will cover patients who wish to self-select to the J-tip or needle group and do not wish to be randomized. These patients will not be in the final analysis. Patients who wish to switch groups after being randomized will be allowed to switch, but will be withdrawn from final analysis. If a patient does not wish to have either method of local anesthesia delivery prior to the regional block, they will be withdrawn from final analysis.

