## **8. Informed Consent Process:**

IRB approval will be obtained prior to patient recruitment. Patients will be identified as they present to the orthopaedic pediatric service of Arnold Palmer Hospital / Orlando Health Inc. with a qualifying injury to determine their interest in participating in the study. The study will be explained to them, they will have an opportunity to read the consent, have their questions answered. If they agree to participate, they will be randomized to a treatment arm as described above.

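### Randomised patients who switch groups are dropped from the final analysis, and no analysis population restores them

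*Combined protocol and SAP*

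**What the plan says.** Section 5 sets the rule for switchers: "Patients who wish to switch groups after being randomized will be allowed to switch, but will be withdrawn from final analysis". It also withdraws patients who decline both methods ("If a patient does not wish to have either method of local anesthesia delivery prior to the regional block") and does not say whether that refusal comes before or after randomisation.

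Section 7 is the whole analysis plan. It covers tests ("To evaluate our hypotheses, we will use exact and non-parametric hypothesis testing procedures"), 95% confidence intervals for differences, and regression where adjustment is thought necessary. It names no as-randomised, intention-to-treat, per-protocol or sensitivity population, and no other section restores the withdrawn patients.

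Section 4 schedules the pain scores whichever method is used: "Visual analogue pain scales will be completed prior to and immediately after J-tip use or needle local anesthesia infiltration", and "The scale will be completed once again prior to and immediately after needle introduction for each regional blockade".

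The 15 extra places are described in three ways. Section 1.4 says "An additional 15 patients will be enrolled to account for withdrawals, bringing total enrolled to 115". Section 5 says they "will cover patients who wish to self-select to the J-tip or needle group and do not wish to be randomized". Section 8 says of consenting patients "If they agree to participate, they will be randomized to a treatment arm as described above".

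**The concern.** Randomisation makes the two groups comparable only while everyone randomised stays in the comparison. This rule removes patients for something that happens afterwards. A wish to switch implies that the arm is known, and the endpoint is the patient's own pain score, so removal can depend on both the arm and the likely outcome.

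The direction cannot be predicted. Some patients may want to avoid the needle; others may be put off by the J-Tip's noise and spray, which Section 4 describes. A randomised patient who declines both methods raises the same problem. Regression adjustment does not help, because it cannot bring back patients who are not in the data set.

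At stake are the primary comparison (pain from the nerve block) and the secondary one (pain from the local injection). Leaving out self-selectors who were never randomised is not a fault.

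**Working it through.** **Plan's own figures.** Section 1.4: 2 × 50 + 15 = 115, which reproduces. Results, Table 1: 54 needle + 57 J-Tip = 111. The t-tests in Table 2 reproduce from Table 1: femoral t = 5.79 pooled and 5.74 Welch; sciatic t = 5.08 pooled.

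**How many could be missing.** If 115 were randomised (an assumption; Section 1.4 gives planned enrolment), 115 − 111 = 4. If some of the 115 were never-randomised self-selectors, fewer than 4 are missing.

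**Size of a selective loss (simulation).** Assumptions: SD 2.3; correlation between fear and pain 0.3 to 0.5; the most fearful patients leave; 54 and 57 remain; two-sample t-test; 100,000 runs per scenario. The SD comes from Table 1. Pooled SD = √[(53·s₁² + 56·s₂²)/109], which gives 1.85 (femoral) and 2.31 (sciatic). No SD is given for block pain.

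| Lost | Bias (needle minus J-Tip) | Null rejection | Power at a true 1-point benefit |
|---|---|---|---|
| none | 0 | 5% | about 64% |
| 1 needle | −0.03 to −0.05 | – | – |
| 4 needle | −0.09 to −0.16 | 5.7% to 6.8% | 49% to 54% |
| 4 J-Tip | +0.09 to +0.15 | 5.7% to 6.8% | 70% to 75% |
| 2 from each | about 0 | 5.2% to 5.4% | about 63% |

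With SD 1.85, losing 4 from one arm gives a bias of 0.07 to 0.13. A simpler formula agrees: shift = (k/n) × D, where D is the mean difference between those removed and those who stay. With k = 4, n = 57.5 and D = 2 (assumed), the shift is 0.14. With SD 2 and 50 per arm, SE = 2·√(2/50) = 0.40 and null rejection is 6.4%.

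**Worst case for the local-injection results.** Missing needle patients are scored 0 and missing J-Tip patients 10 on an assumed 0–10 scale, over every split of 4. The worst split puts all 4 in the J-Tip arm.
- Femoral: 3.57 − (57 × 1.54 + 4 × 10)/61 = 3.57 − 2.095 = 1.475; Welch p = 0.0011.
- Sciatic: 4.50 − (57 × 2.272 + 4 × 10)/61 = 4.50 − 2.779 = 1.721; Welch p = 0.0007.
- If 115 is not the ceiling, the femoral result holds with 8 missing (p = 0.044) and is lost with 9 (p = 0.079). The sciatic result holds with 10 (p = 0.047) and is lost with 11 (p = 0.072).

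This covers the t-tests only. The adjusted regressions have 106 total degrees of freedom, so N = 107, which is 8 short of 115. Nothing links those 4 further patients to the switching rule.

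**Block pain (primary).** The Results list it only among the non-significant variables, without means or SDs. Two bounds are still possible.
- Four patients can move the difference by at most max over k of 10k/(54+k) + 10(4−k)/(61−k). At k = 3 this is 30/57 + 10/58 = 0.70.
- With 54 and 57 patients, a difference is non-significant below about 0.70 (SD 1.85) or 0.87 (SD 2.3). With 4 extreme scores added in favour of the J-Tip, the smallest observed difference that becomes significant is 0.32 to 0.42 (SD 1.85) or 0.45 to 0.57 (SD 2.3), for assumed means of 2 to 5.

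**The case against.** The strongest reply is about size. The documents do not show that anyone switched, and without switchers or refusers the rule does no harm. The largest illustrative bias, 0.16 points, needs all 4 missing patients to come from one arm and to be the most fearful in it, with a correlation of 0.5. One lost patient, or an even split, makes almost no difference. Section 4 also ties sedation before the injection to anxiety scores, which may weaken any link between fear and pain. The Results report no significant difference between arms in VAS before the local injections or in sedation. Finally, analysis as randomised dilutes the contrast between the methods actually received.

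The points on size stand: these figures do not show that a reported result is wrong. They do not remove the defect. The rule is explicit, and nothing in the plan limits how many patients it may remove. Non-significance among those analysed is not evidence of balance, and it says nothing about those excluded. The nervousness score is not in that list. The missing counts and block-pain figures are what a reader would need to dismiss the worry. The dilution is real but small.

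**Conclusion.** The concern holds. As written, the plan breaks the as-randomised comparison whenever a randomised patient switches, or declines both methods after randomisation. The bias can go either way, and its true size is unknown because the numbers randomised, switched and refused are not reported by arm.

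On the assumption that 115 were randomised, the plausible effect is small, and the unadjusted local-injection differences are robust to it. The primary block-pain result cannot be cleared in the same way. Under the assumed SDs and means, 4 missing patients could turn it significant only if the observed difference was already at least about 0.3 to 0.6 points, and that difference is not given. This should be fixed, but it does not by itself overturn the reported findings.

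A lesser point of wording: it is unclear whether the 15 extra places also cover randomised losses.

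**What to change.** Replace the Section 5 rule, and add to Section 7, wording such as: *All randomised patients with the relevant VAS are analysed in the group to which they were randomised, whatever method they received. Exclusion of switchers, and analysis by method received, are sensitivity analyses only.*

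- Keep collecting VAS scores from switchers.
- Keep a patient who declines both methods after randomisation in the block-pain analysis if that score exists, and report the patient as missing for local-injection pain.
- Report numbers randomised, switched and refused by arm, with reasons.
- State whether the 15 extra places cover randomised losses, never-randomised self-selectors, or both.

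If enrolment is complete, report those counts, re-analyse as randomised where the scores were kept, and give block-pain means, SDs and 95% confidence intervals by arm.

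The cost is a change of wording, or a flow table and a short re-analysis. Scores from withdrawn switchers may not have been kept, in which case the counts are the minimum. The statistical price is dilution: 2.03 × (1 − 1/57) = 1.99 if 1 of 57 in one arm switches, and 2.03 × (1 − 4/57) = 1.89 if 4 do.
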